8.2.3.2. Adverse Events

• All adverse events

The number and proportion of patients with adverse events will be tabulated by SOC and PT.

• Adverse events by serious/non-serious

The number and proportion of patients with serious adverse events will be tabulated by SOC and PT. The same tabulation will be performed for non-serious adverse events.

8.2.3.3. Other Endpoints

• Laboratory test values

In patients with hepatic toxicity, an adverse drug reaction considered as a major investigation item, summary statistics of the values of laboratory parameters related to hepatic function (AST, ALT, Al-P, and γ -GTP) at the initiation of treatment, the onset of the adverse drug reaction, and the completion of treatment will be calculated by change in treatment with Vfend. A1.1 Definition of Visit Timing of Appendix 10.1 will be followed for values at the initiation and completion of treatment. The value immediately before the day of onset of adverse drug reaction after the day of initiation of Vfend treatment will be used as the value at onset.

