#### 7.9. Limitations of the research methods

The following matters are considered for this study:

- 1) Since no control group is set in the study, there is a limit to the judgment on whether or not a risk of developing adverse events and adverse reactions increases due to the administration of the study drug.
- 2) The consideration for confounding factors may not be adequate because the background information may not be sufficiently obtained.
- 3) Since this is a study that collects the information described in medical charts, the set data may not be collected or there may be missing information.

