8. STATISTICAL METHODS AND STATISTICAL ANALYSIS

8.1. Statistical Methods

8.1.1. Analysis of Continuous Data

Summary statistics (number of patients, mean, standard deviation, median, maximum, and minimum) will be calculated.

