9. LISTINGS

The following listings will be prepared. Listings with [Intext] specified after the table name are in a format which allows attachment to the report.

Listing of patients⁴

⁴: Estimated creatinine clearance and eGFR before administration will be added to the patient listing. Refer to Appendix 10.3 for calculation method.

- Listing of patients with adverse events
- Listing of patients with adverse drug reactions
- Listing of patients with adverse drug reactions among pediatric patients
- Listing of patients with adverse drug reactions among elderly patients
- Listing of patients with adverse drug reactions among patients with hepatic dysfunction
- Listing of patients with adverse drug reactions among patients with renal dysfunction
- Listing of patients with adverse drug reactions among patients excluded from the safety analysis set
- Listing of patients with serious adverse drug reactions [Intext]
- Listing of deaths [Intext]
- List of events corresponding to safety specifications
- List of adverse drug reactions falling under safety specifications [Intext]
- Listing of laboratory values
- Listing of patients evaluated for effectiveness
- Listing of the status of treatment of Vfend and plasma voriconazole concentration
- List of contraindicated patients
- Listing of prior treatment (antifungal agents administered for prophylaxis of invasive fungal infections)
- Listing of other reasons for discontinuation [Intext]
- Listing of concomitant medications by patient [Intext]

Furthermore, tables corresponding to appendix tables for periodic safety report (PSUR) and application for reexamination will be prepared in accordance with the notification.

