10. APPENDICES

10.1. Appendix 1: Details of Data Extraction

A1.1 Definition of Visit Timing

Visit timing	Endpoint	Definition [acceptable range]
Before initiation of treatment	Laboratory test	From 30 days before the day of initial dose in this study (day of initiation of treatment)] to the day of initiation of treatment. If there are multiple days, the date closer to the day of initial dose will be adopted.
At completion of treatment	Laboratory test	On or after the day of last dose in this study. If there are multiple days, the date closer to the day of last dose will be adopted.

10.2. Appendix 2: Examples of Risk Ratio of Incidence of Adverse Drug Reactions by Subgroups

Event name: XXX increased	Category 1		Category 2.		Risk ratio (RR)=	
ø	Number of patients/N-	(%)~	Number of patients/Ne	(%)~	RR-	95 %CI~
Gender (male vs. female)-	18/2220.0	-(0.8)	3/1099.	(0.3)	2.97.	(0.88- 10.06)-
≥65 years vs. <65 years	19/2788-	(0.7)-	2/531-	(0.4)-	1.81-	(0.42=7.74)
Diagnosis (Disease A vs. Disease B)-	3/221-	(1.4)-	18/3 098-	(0.6)-	2.34-	(0.69-7.87)-
Duration of illness (<1 year vs.≥1 year).	9/771-	(1.2)-	7/8:66-	(0.8)	1.44-	(0.54 -3.86)-
Drug A Concomitant use (present ws. absent)-	9/798-	(1.1)-	12/2.521	(0.5)-	2.370	(1.00-5.60)
Drug A Prior treatment (present vs. absent).	1/148	(0.7)-	20/3171-	(0.6)	1.07-	(0.14-7.93)-
Disease B Complications (present vs. absent).	16/1614-	(1.0)-	5/1703-	(0.3)	3.38-	(1.24-9.20)-
Disease B Past medical history (present vs. absent).	7/674	·-(1.0)	14/2:643.	(0.5)	1.96-	(0.79-4.84).
Hepatic dysfunction (present vs. absent)-	0/80-		18/2:056-	(0.9)-	÷	4 ²
Renal dysfunction (present vs. absent)-	1/140	(0.7)-	17/2:004->	(0.8)-	0.84-	(0.11-6.28)

Incidence of Adverse Drug Reaction

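### Liver tests in hepatic-toxicity patients are summarised as three separate columns with no within-patient change, so patient mix or starting level can pass for a rise, a recovery or a group difference (minor)

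*SAP*

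**What the plan says.** SAP 8.2.3.3 sets the population and content: "In patients with hepatic toxicity, an adverse drug reaction considered as a major investigation item, summary statistics of the values of laboratory parameters". The tests are AST, ALT, Al-P and γ-GTP, and the statistics for their levels "at the initiation of treatment, the onset of the adverse drug reaction, and the completion of treatment will be calculated by change in treatment". That last phrase refers to the action taken with Vfend, whose five categories are given in SAP 8.2.3.1: discontinuation, temporary discontinuation, dose reduction, dose increase and no change. It is not a change in the laboratory value.

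The statistics come from SAP 8.1.1: "Summary statistics (number of patients, mean, standard deviation, median, maximum, and minimum) will be calculated". Neither section mentions a within-patient difference, a ratio to the starting value, or a restriction to patients who have more than one of the values. No such analysis appears elsewhere in the SAP.

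Each time point has its own selection rule:

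- Initiation (SAP Appendix 1): "From 30 days before the day of initial dose in this study" up to the day treatment starts, taking the closest test.
- Onset (SAP 8.2.3.3): "The value immediately before the day of onset of adverse drug reaction after the day of initiation of Vfend treatment".
- Completion (SAP Appendix 1): "On or after the day of last dose in this study", taking the closest test, with no upper limit.

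Protocol 7.9 warns that, with chart data, "the set data may not be collected or there may be missing information". SAP 9 includes a "Listing of laboratory values".

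**The concern.** The values are repeated measurements in the same patients, but the table treats each time point as a column of its own. If the columns hold different patients, moving from one to the next mixes the change within patients with a change in who is being measured. The table cannot separate the two.

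Hepatic toxicity is a major investigation item. Protocol 7.3.8 and SAP 2.1 ask how patients who could continue the product differ from those who had to stop, and this is the only planned summary of laboratory values for that item. A reader will use it to judge whether enzymes rose, whether they came back, and whether this differed by action taken. Raw columns can mislead on all three.

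**Working it through.** **1. Who is in the table.** Inputs from the sample-size rationale (Protocol 7.5.2, repeated in SAP 2.1): 200 patients and 20% incidence, so 200 × 0.20 = 40 expected cases. The plan states at least 31 cases with a probability of about 95%. The exact binomial gives P(X ≥ 31) = 0.957 (0.972 for 30, 0.937 for 32), so the plan's figure reproduces.

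**2. How small the groups may be.** The same section gives discontinuations among hepatic cases in three studies: 1/47, 2/11 and 2/4, pooled 5/62 = 8.1%. Two studies count the hepatobiliary SOC and the third counts hepatic toxicity including abnormal tests, so pooling is only a rough guide.

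- 31 × 5/62 = 2.5 patients; 40 × 5/62 = 3.2 patients.
- Extremes: 31 × 1/47 = 0.7 and 40 × 2/4 = 20.

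The discontinuation group may therefore hold only two or three patients, and the others are spread over four further categories.

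**3. Who can appear in each column.**

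| Column | Test needed | Who is left out |
|---|---|---|
| Initiation | Day −30 to the start day | No chart test in that window |
| Onset | After the start day, before the onset day | Early onset with no test in between |
| Completion | On or after the last dose | No test from that day on |

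The completion rule has a further difficulty. SAP 6.1 takes laboratory values up to the end of the observation period, and SAP 2.1 ends that period on the day treatment is completed. On that reading, a routine completion value exists only if a test fell on the last-dose day, and later values would come mainly from adverse-event follow-up. The documents do not settle this, but it is another way for the completion column to hold a selected group.

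**4. Effect of patient mix.** Suppose nobody's value changes. A fraction f of patients has no later test, and their starting level is d SD above that of the others, whose mean is m.

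- Mean of the initiation column: (1 − f)·m + f·(m + d) = m + f·d
- Mean of the later column: m
- Apparent change: −f·d SD, although the true change is zero

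The documents give neither f nor d. Under assumed ranges:

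| f | d = 0.5 | d = 1.0 |
|---|---|---|
| 10% | −0.05 | −0.10 |
| 25% | −0.125 | −0.25 |
| 40% | −0.20 | −0.40 |

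This would read as a recovery. If the untested patients start lower, the sign reverses and it reads as a rise. In this example, taking the change in patients with both values returns zero.

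**5. Effect of starting level.** On any additive scale (logs, for ratios), later level = starting level + change. The difference in later level between patients who stopped and those who continued is therefore the difference in starting level plus the difference in change. Unequal starts are plausible: Protocol 7.3.1 records existing hepatic disorder and its severity at baseline, and 7.3.8.1.1 counts aggravation as well as new occurrence. The initiation column allows a correction only where the same patients fill both columns; otherwise the shift in step 4 enters each group separately.

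**6. Complete data.** If every patient has both values, the difference between the two column means equals the mean within-patient difference, and the patient-mix problem vanishes. The columns still do not show how changes vary between patients.

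**7. What the onset value measures.** By rule it precedes the day of onset. Protocol 7.3.8.1.1 names ALT, AST and GGT increases as hepatic toxicity. Where such a reaction is dated to the test that revealed it, that test falls on the onset day and is not selected. A ratio of onset to initiation can then compare two pre-event values and miss the rise.

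**The case against.** The case against is substantial. The study is not confirmatory (SAP 4.1), and 8.1.1 plans no test or confidence interval on these values. The n per column is reported, so unequal columns can be noticed. Initiation values stand in the same table by the same groups, so unequal starting levels can be seen. SAP 8.2.3.1 also tabulates hepatic toxicity by outcome and action taken, and compares patients who stopped with those who did not on background, concomitant medication and administration status. Protocol 7.3.8 names background and dose as the differences to examine, not the size of the enzyme change. The laboratory listing would let someone derive within-patient changes for some 31 to 40 cases.

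Most of this stands, and it limits the severity. It does not remove the point. An n per column shows that the patient sets differ in size, not which patients differ or what that does to the means. A derivation from the listing would be unplanned.

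A reader might go further and infer that the separate columns lose much precision, or attach power or false-positive figures to them. The documents do not support that. No test is planned. With complete data the mean change is the same number either way, and only its standard error cannot be recovered. Any figure would need a within-patient correlation that the documents do not give. A calculation on all 31 cases would also fit no cell of a table split by action taken. No such claim is made here.

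The objection that a ratio would formalise a misleading onset value is correct, and the fix has to deal with it.

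**Conclusion.** The point holds as a minor one. As written, the table cannot separate a change within patients from a change in who was tested, or a group difference in change from a difference in starting level. This follows from the text: no within-patient measure, three different selection rules, and missing chart data acknowledged in the protocol.

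Its size cannot be derived from the documents. The 0.05 to 0.40 SD shift illustrates assumed missingness and starting-level differences; it is not an estimate. With complete data in every group, the patient-mix part would be nil.

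Two limits apply to any improvement. The group of patients who stopped may be too small for a summary to say much, and the onset value cannot describe the size of the rise while it is taken from before the event.

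**What to change.** In SAP 8.2.3.3, for each parameter and change-in-treatment group:

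- Add the within-patient ratio to the initiation value, for completion/initiation and onset/initiation, in patients with both values. Give the median and range, or the geometric mean, and show the paired n.
- Where a group has 5 or fewer patients, show the individual ratios without a confidence interval, in line with the SAP's own rule for binary comparisons in 8.1.3.
- Keep the raw-value columns as description.
- Label the onset/initiation ratio as a pre-onset change, or revise the definition of the onset value so that it reflects the event, before using it to describe the size of the rise.

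The cost is one added block in an existing table and no new data. The downside is that patients without both values do not enter the ratio, and some selection on who was tested remains. Showing the paired n beside the column n makes that visible.

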#### (1) Hepatic toxicity

For patients who developed events related to hepatic toxicity including abnormal hepatic function test values, assess the occurrence status and the differences in patient background, dose, etc. between patients who can be continuously administered this product and patients who must be discontinued administration of this product.

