# 7.3.8.1. Confirmation of presence/absence of adverse events that correspond to major investigation items

# 7.3.8.1.1. Presence/absence of hepatic toxicity

The presence/absence of hepatic toxicity including hepatitis, jaundice, hepatic failure, coma hepatic, ALT (GPT) increased, AST (GOT) increased, and GGT increased should be recorded for target patients in this study. If aggravation or new occurrence of hepatic toxicity is observed, the information in detail should be recorded in the adverse event column.

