#### Abnormal test findings

The criteria for determining whether an abnormal objective test finding should be reported as an adverse event are as follows:

- Test result is associated with accompanying symptoms, and/or
- · Test result requires additional diagnostic testing or medical/surgical intervention, and/or
- Test result leads to a change in study dosing or discontinuation from the study, significant additional concomitant drug treatment, or other therapy, and/or
- Test result is considered to be an adverse event by the investigator or sponsor.

Merely repeating an abnormal test, in the absence of any of the above conditions, does not constitute an adverse event. Any abnormal test result that is determined to be an error does not require reporting as an adverse event.

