	8.2.3.3. Other Endpoints
	- It was changed to calculate summary statistics by timing of onset of adverse drug
	reactions of hepatic toxicity in patients who experienced adverse drug reactions of hepatic
	toxicity from the time plots of each laboratory parameter.

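### The liver-test value at onset in SAP 8.2.3.3 is taken from before the day of onset, so a laboratory event dated to its abnormal test loses that test from the onset column

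*SAP*

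**What the plan says.** SAP 8.2.3.3 (Laboratory test values) plans summary statistics for four liver tests in patients whose adverse drug reaction is hepatic toxicity. The time points are the start of treatment, "the onset of the adverse drug reaction, and the completion of treatment will be calculated by change in treatment with Vfend". For the first and last of these it refers to Appendix 10.1, A1.1. For the middle one, the onset value, it gives its own rule: "The value immediately before the day of onset of adverse drug reaction after the day of initiation of Vfend treatment will be used".

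A1.1 has two rows, and each includes its anchor day. The pre-treatment window runs from 30 days before the first dose "to the day of initiation of treatment. If there are multiple days, the date closer to the day of initial dose will be adopted". The completion value is taken "On or after the day of last dose in this study". There is no row for onset.

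The protocol treats laboratory findings as hepatic toxicity. Section 7.3.8 (1) concerns "events related to hepatic toxicity including abnormal hepatic function test values". Section 7.3.8.1.1 names clinical diagnoses and also laboratory terms: "ALT (GPT) increased, AST (GOT) increased, and GGT increased should be recorded for target patients in this study". Under abnormal test findings in Section 9.4.1, one sufficient criterion is: "Test result is considered to be an adverse event by the investigator or sponsor". Section 7.3.7 collects the date of occurrence of every adverse event and, for those tied to a laboratory change, also the test date and result. It does not say how the two dates relate.

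**The concern.** For a clinical event such as jaundice, the last sample before onset may be a reasonable description of the patient at onset. For a laboratory-defined event the abnormal result is the event. If the investigator dates the event to that test, the SAP rule excludes the one result that defined it. The column labelled onset then shows the previous on-treatment value, which understates the abnormality whenever that value was lower. If the abnormality appeared at the first on-treatment sample, the column has no value.

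Hepatic toxicity is one of the study's two major investigation items, and the protocol asks how patients who could continue differ from those who had to stop. This table is the only planned liver-test summary split by change in treatment. The SAP's version 3.0 change log says of this section: "It was changed to calculate summary statistics by timing of onset of adverse drug" reactions, in place of time plots of each laboratory parameter. No planned plot would therefore show the displaced values.

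**Working it through.** **1. The plan's own figure.** Protocol 7.5.2 and SAP 2.1 assume 200 patients and 20% hepatic toxicity, and state that at least 31 cases will be seen with probability of about 95%.

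- Expected cases: 200 × 0.20 = 40.
- X ~ Binomial(200, 0.20): P(X ≥ 31) = 0.957 (0.972 for 30, 0.937 for 32). The stated figure is reproduced.
- Central 95% range: 29 to 51 cases.

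So this table should hold about 40 patients. SAP 8.2.3.1 names five change-in-treatment categories, which gives 40 / 5 = 8 per category if they were evenly filled (an assumption; they need not be).

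**2. The rule as written.** Eligible samples satisfy: initiation day < sample day < onset day, and the latest is taken. The alternative that includes the onset day is: initiation day < sample day ≤ onset day, latest taken.

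**3. Both rules on an assumed schedule** (initiation Day 1; samples on Days 8, 15, 22 and 29; the schedule is not from the documents):

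| Case | Abnormal test | Onset dated | Rule as written | Onset day included |
|---|---|---|---|---|
| A | Day 22 | Day 22 | Day 15 | Day 22 |
| B | Day 22 | Day 23 | Day 22 | Day 22 |
| C | Day 8 | Day 8 | none | Day 8 |
| D | Day 22 | Day 26 | Day 22 | Day 22 |

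With assumed ALT values of 30, 38, 180 and 240 U/L on the four sample days, case A enters the onset column as 38 under the present rule and as 180 when the onset day is included. Cases B and D show that an event dated after its abnormal test is already handled correctly.

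**4. A two-sided window.** Taking the closest value on either side of onset also returns the abnormal test in cases A to C. In case D it does not: Day 29 is 29 − 26 = 3 days away and Day 22 is 26 − 22 = 4 days away, so it takes Day 29. That value is post-onset and may follow the very treatment change by which the table is split. Including the onset day and looking back returns the abnormal test in all four cases.

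**5. How many patients.** The number affected is s × 40, where s is the share of hepatic cases that are laboratory-defined and dated to the day of the abnormal test. The documents give no value for s. For scale only, s = 0, 0.25 or 0.50 gives 0, 10 or 20 patients.

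**The case against.** The strongest reply is that the effect may be nil. If sites date onset after the test, for example to the day the result was reviewed, the rule works. The SAP may also have meant to include the onset day: both A1.1 windows include their anchor days, and the English may have lost the equivalent of *on or*. The study is non-confirmatory (SAP 4.1) and only one descriptive column is involved. The comparison of continuing with discontinuing patients is made mainly through background, concomitant medication and administration status in SAP 8.2.3.1, none of which uses the onset value.

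Most of this stands, and it limits the size of the point. It does not remove it. The text says before the day of onset, nothing elsewhere restores that day, and a programmer following it would exclude the onset-day sample. If inclusion was intended, the same phrase has to be added.

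A reader might infer that all 40 expected onset values, or all 31 at the plan's floor, would be wrong. The documents do not support that. Protocol 7.3.8.1.1 also lists hepatitis, jaundice, hepatic failure and hepatic coma, which need not be dated to a test. Two of the three rates behind the 20% assumption (47/233 and 11/45) count reactions in the hepatobiliary system organ class; only the 4/21 from the paediatric study is described as including abnormal liver test values.

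**Conclusion.** The point holds as a rule that gives the wrong value when applied literally to a laboratory-defined hepatic event dated to its abnormal test. The onset column then carries the preceding on-treatment result or none. This rests on the literal reading of SAP 8.2.3.3 and on at least some events being dated that way; the documents do not settle the second condition. The share is therefore unknown, possibly zero, and confined to laboratory-dated events among about 40 expected hepatic cases.

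A reader might also infer that the hepatic safety results as a whole are compromised. They are not. Incidence, outcome and time to onset do not use this value, the initiation and completion columns have their own rules, and the listing of laboratory values in SAP 9 keeps the raw results, so the table could be recalculated. The correction is worth making because it is cheap and the table serves a major investigation item.

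**What to change.** In SAP 8.2.3.3, and as a new onset row in A1.1, define the onset value as *the result on the day of onset or, if there is none, the last result before it, in either case after the day of initiation*. Report the number of patients with no such value, by change-in-treatment category. If a pre-onset value is really what is wanted, keep the rule and relabel the column *last value before onset*.

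The cost is one phrase, one appendix row and a one-character change in the date comparison. No new data are needed, since Protocol 7.3.7 already collects occurrence dates, test dates and results. A wider two-sided window is not needed and could bring in results from after the treatment change. One limit remains: if onset is dated before the first abnormal test, the amended rule still shows the earlier result.
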